Parkinson's disease (PD) is a devastating neurodegenerative disease affecting ~1 million Americans with ~60,000 new diagnoses made annually¹. There are no interventions that slow the inexorable progression of PD. Thus, there is a ***critical need*** to develop novel disease-modifying therapies for PD. We have discovered that activation of phosphoglycerate kinase 1 (Pgk1) can reverse energy deficits that contribute to the pathology of PD. More importantly, we have discovered that terazosin (TZ) can activate Pgk1 through a novel mechanism that is independent of its predicted α -adrenergic receptor antagonism and slow the progression of PD. The procedures outlined in the protocol will allow us to 1) quantify energy deficits in the brains of patients with PD and 2) determine if the administration of TZ can alter energy deficits over a short time period and longer time period. **This study will test the safety and tolerability of TZ in patients with PD as well as test the feasibility of this protocol while providing vital information to guide future clinical trials of TZ in PD.**

Study Title

A FeASibiliTy study of TeraZosin as a disease modifying treatment for PD: FAST TZ-PD

Objectives

Primary objective:

To assess the safety of TZ in patients with PD as well as the feasibility of the study protocol. The active treatment group (TZ 5mg daily) will be compared to a placebo group. The primary outcome measure will be the safety and tolerability of TZ in the select patient population. This will be assessed by comparing the number of participants in each group that experience drug-related adverse drug events as well as assessing the rate of drop out in each group.

Secondary objective:

Orthostatic hypotension is more common in PD², so it is possible that TZ could exacerbate this symptom of PD. To assess the change in blood pressure (systolic and diastolic) from baseline to week 6 and from baseline to week 12.

Exploratory Objective:

[figure not shown]
To quantify ATP levels in 1) red blood cells and 2) in the brain before and after the administration of TZ and after taking TZ for 12 weeks.

Design and Outcomes

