1.3 Exploratory Objectives

- 1) To utilize magnetic resonance spectroscopy (MRS) to quantify ATP levels in the brain at baseline, after a single dose of study drug, and after 12 weeks of treatment with study drug
- 2) To explore the effect of TZ on ATP levels in red blood cells.

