6.2 Timing of Study Activities

6.2.1 Screening/Pre-Randomization Evaluations/procedures

Individuals identified at each site to potentially be eligible for inclusion will first be informed about the study and asked if they wish to receive more information. If the subject answers in the affirmative, approved staff will first go through the informed consent document with the subject and answer any questions that the subject may have. Specifically, the participant will be informed that signing this informed consent document does not guarantee that they will be included in the study. It simply allows the study sites to perform the necessary screening procedures to determine if the participant is eligible for randomization. If the participant signs the informed consent document, the participant will then be screened. This will include the following assessments:

- Review of inclusion/exclusion criteria
- Documentation of PD
- Hoehn & Yahr
- Review of concomitant medications/prohibited medications
- Orthostatics
- Medical history
- A physical exam
- Neurological exam
- Body weight and height
- Vital signs
- MDS-UPDRS Motor assessment
- Beck Depression Inventory, Beck Anxiety Inventory, Columbia-Suicide Severity Rating Scale

If the participant is found to be eligible for randomization based on this screening visit, their first baseline visit will be scheduled. The baseline visit must be scheduled within 90 days of the initial screening visit. If the participant is unable to schedule their baseline visit within 90 days of the screening visit, they may still be eligible for inclusion, but they will need to be re-screened.

After all assessments are completed, the site investigator will review the available data and ensure that the participant is eligible for randomization. If so, the participant will be randomized at Day 1. They will then be dispensed their study treatment packs. The participants will then have their blood drawn and then have their MRI. Immediately following this initial MRI, they will take their first dose of TZ 1mg or placebo. They will then wait 3 hours from that time, during which the other study assessments may be completed. After three hours from the time that they took their TZ, they will have their blood drawn again, and will then undergo another MRI study.

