6.3.9 Laboratory Evaluations

Women of child-bearing potential will have a urine-dipstick pregnancy test performed at their screening visit, their baseline/randomization visit, and at their 6 week visit. The site PI must verify each result and indicate that the results are “Negative” or “Positive”. If the results are “negative”, this indicates that the subject is not pregnant. If the results are “positive” this indicates that the subject is pregnant and must discontinue study drug.

The MRI studies are being conducted to perform MR Spectroscopy in an attempt to quantify ATP levels in the brain.

The blood draws are being conducted to collect red blood cells. These samples will be sent immediately to the lab of [name], where they will be analyzed to quantify ATP levels in the red blood cells.

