9.4 Data Analyses

The following outcome measures will be analyzed under an intention-to-treat protocol. All randomized individuals will be included regardless of their final treatment status.

- Primary Outcome
 - Rate of drop out between groups
 - Chi-square
 - Rate of adverse events between groups
 - Chi-square
- Secondary outcomes
 - Prevalence of orthostatic hypotension between placebo and active group
 - Chi-square
 - Prevalence of falls between placebo and active group
 - Chi-square
 - Differences in overall compliance between placebo and active group
 - Linear mixed effect models that includes compliance at each study visit for each participant
- Exploratory outcomes
 - Difference in ATP levels in red blood cells and brain within subjects before and after taking study drug on day 1
 - Paired samples t-test
 - Difference in ATP levels in red blood cells and brain within subjects at 6 and 12 weeks compared to baseline reading

- Paired samples t-test
- Difference in ATP levels in red blood cells and brain between groups at 6 weeks and 12 weeks
 - Independent samples t-test
- Slope of change over 12 weeks of the MDS-UPDRS Part 1
 - LMER
- Slope of change over 12 weeks of the MDS-UPDRS Part 2
 - LMER
- Slope of change over 12 weeks of the MDS-UPDRS Part 3
 - LMER
- Slope of change over 12 weeks of the MDS-UPDRS Part 4
 - LMER
- Absolute change over 12 weeks of the MDS-UPDRS Parts 1, 2, 3, 4, and TMS
 - Independent samples t-tests
- Slope of change over 12 weeks of MDS-UPDRS TMS (direct comparison for efficacy)
 - LMER
- Slope of change over 12 weeks of the Hoehn & Yahr Score
 - LMER
- Slope of change over 12 weeks of all cognitive assessments between placebo and active group
 - LMER
- Slope of change over 12 weeks of sleep assessments between placebo and active group
 - LMER
- Slope of change over 12 weeks of behavioral assessments between placebo and active group
 - LMER

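### Day 1 ATP is tested only within subjects, although placebo is re-measured too, and week-6 brain ATP is listed with no week-6 MRI scheduled

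*Combined protocol and SAP*

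**What the plan says.** Section 9.4 lists three exploratory ATP analyses, and section 9.1.3 lists the same three outcomes:

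- (a) "Difference in ATP levels in red blood cells and brain within subjects before and after taking study drug on day 1", by paired t-test;
- (b) "Difference in ATP levels in red blood cells and brain within subjects at 6 and 12 weeks compared to baseline reading", by paired t-test;
- (c) "Difference in ATP levels in red blood cells and brain between groups at 6 weeks and 12 weeks", by independent-samples t-test.

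For (a) and (b) the plan does not say whether the test is run in each arm or over both arms pooled.

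Section 6.2.1 describes Day 1. After the first blood draw and scan, "Immediately following this initial MRI, they will take their first dose of TZ 1mg or placebo". Three hours later "they will have their blood drawn again, and will then undergo another MRI study".

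On the source of brain ATP, section 6.3.9 states: "The MRI studies are being conducted to perform MR Spectroscopy in an attempt to quantify ATP levels in the brain". The MRI row of the Schedule of Activities (section 6.1) is marked at Day 1 and week 12 only. Section 1.3 matches it: the aim is to "quantify ATP levels in the brain at baseline, after a single dose of study drug, and after 12 weeks of treatment". The blood-draw row is marked at Day 1, week 6 and week 12.

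The opening summary says the procedures will "determine if the administration of TZ can alter energy deficits over a short time period and longer time period".

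**The concern.** Analyses (a) and (b) use the baseline but not the placebo arm. Analysis (c) uses the placebo arm but not the baseline. At weeks 6 and 12 this matters little, because (c) is a valid randomised comparison. On Day 1 nothing stands beside (a), so the single-dose question has no controlled test.

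A paired test asks whether ATP changed between two measurements. It cannot say why. Anything that moves both arms between them (a repeat scan, time of day, rest) counts toward the result. Day 1 is the only single-dose measurement and the only one that serves the short-period aim. The pilot is meant to guide later trials, so a Day 1 signal that cannot be attributed to terazosin (TZ) could mislead their design.

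The second problem is one of consistency: week-6 brain ATP is listed both within subjects and between groups, with no scan to supply it.

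**Working it through.** **Listed tests against scheduled data**

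| Measure | Time | Data scheduled in both arms? | Between-arm test listed? |
|---|---|---|---|
| Red-cell ATP | Day 1, 3 h after dose | Yes | No |
| Brain ATP | Day 1, 3 h after dose | Yes | No |
| Red-cell ATP | Week 6 | Yes | Yes |
| Brain ATP | Week 6 | No MRI | Yes |
| Red-cell and brain ATP | Week 12 | Yes | Yes |

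**Inputs.** There are 10 patients per arm, allocated 1:1 (Sample Size and Population; section 4.5.4). Section 9.2 bases the sample size on funding and resources, so there is no power figure to reproduce. The documents give no alpha, SD, drift or repeatability for ATP. Assumed here: two-sided 5%, complete data, equal SDs in the two arms, and a range of drifts and correlations.

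**1. False positives of the Day 1 paired test.** Suppose the drug has no effect and both arms drift by d, in SDs of within-person change. The paired statistic is then noncentral t with n − 1 degrees of freedom and noncentrality d√n. At n = 10 and d = 0.5 the noncentrality is 0.5 × 3.162 = 1.58.

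| Drift d | 0.1 | 0.25 | 0.5 | 0.75 | 1.0 |
|---|---|---|---|---|---|
| TZ arm alone, n = 10 | 0.059 | 0.109 | 0.293 | 0.562 | 0.803 |
| Arms pooled, n = 20 | 0.071 | 0.186 | 0.565 | 0.889 | 0.989 |
| Significant in TZ but not in placebo | 0.056 | 0.097 | 0.207 | 0.246 | 0.158 |

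The last row is p(1 − p), with p from the first row: two independent arms tested separately and the results compared informally. In simulation over drifts of 0.1 to 1.0 SD and correlations of 0.3, 0.5 and 0.8 (20,000 trials), a between-arm ANCOVA rejected in 4.6% to 5.4% of trials.

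**2. What control costs on Day 1.** Let ρ be the correlation between the pre-dose and post-dose values. The differences detectable with 80% power, in SDs of the ATP level, are:

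- paired test in the TZ arm, n = 10, valid only with no drift: 0.996 × √(2(1 − ρ));
- ANCOVA, 17 degrees of freedom: 1.370 × √(1 − ρ²), where 1.370 includes the factor √(1 + 1/16) for chance baseline imbalance.

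| ρ | 0.3 | 0.5 | 0.7 | 0.8 |
|---|---|---|---|---|
| TZ-arm paired | 1.178 | 0.996 | 0.771 | 0.630 |
| ANCOVA | 1.307 | 1.187 | 0.979 | 0.822 |
| ANCOVA larger by | 11% | 19% | 27% | 31% |

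At ρ = 0.9 the excess is about 34%.

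**3. Weeks 6 and 12.** The unadjusted t-test in (c) detects 1.325 SD (18 degrees of freedom). ANCOVA detects the values in the table above, and 1.370 SD at ρ = 0. The standard errors are equal when (1 − ρ²)(17/16) = 1, so ρ = √(1/17) = 0.243. Below that, adjustment costs up to 3% in standard error (√(17/16) = 1.031).

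**The case against.** The strongest reply is that the high error rates describe a careless reading. They apply if the TZ-arm result is taken alone, or the arms are pooled, and the change is credited to the drug. The Day 1 line refers to study drug, which includes placebo, so a placebo result might be shown alongside. On that reading the false-claim rate peaks near 25% in the drifts examined, not 80%. This is fair, but comparing two p-values is still not a test of the difference between arms, and 10% to 25% at drifts of 0.25 to 1.0 SD is well above 5%.

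The drift itself is hypothetical. That stands: nothing in the documents supports a particular size, and at 0.1 SD the paired test is close to nominal. The absence of a controlled Day 1 test does not depend on that assumption.

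Baseline adjustment at weeks 6 and 12 corrects no error. That also stands; it is a precision choice, and it loses slightly if the correlation is low.

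The week-6 brain item looks like a drafting slip, because one bullet covers two tissues and two visits. That is likely, and with no scan no wrong result can follow. It still leaves a listed outcome that cannot be reported.

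Finally, ATP is exploratory, the sample was not powered, and week 12 already has a between-group test. This limits the severity but does not answer the Day 1 gap.

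**Conclusion.** Both parts hold. As written, the plan cannot attribute a Day 1 change in red-cell or brain ATP to TZ, although the placebo measurements needed to do so are collected. The gap is documented; the size of any bias is not. Under assumed drifts of 0.1 to 1.0 SD of change, the paired test's false-positive rate runs from 6% to 80% in one arm and from 7% to 99% pooled, against about 5% for a between-arm test.

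Week-6 brain ATP has no scheduled data source; week-6 red-cell ATP does.

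The change should be made, but the consequence is confined to exploratory outcomes. The primary safety and tolerability analysis is not affected.

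**What to change.** 1. In sections 9.1.3 and 9.4, add a Day 1 comparison between arms for red-cell and brain ATP: ANCOVA of the 3-hour value on the pre-dose value and arm, reported as an adjusted difference with a 95% confidence interval.
2. Use the same model at week 6 (red-cell ATP only) and week 12 (both) for consistency and probable precision. This step is optional in a way that the first is not.
3. Keep the paired changes, on Day 1 and at weeks 6 and 12, as descriptive summaries by arm, not pooled.
4. Reconcile the week-6 brain ATP wording in sections 9.1.3 and 9.4 with the Schedule of Activities and section 1.3. Removing brain ATP from the week-6 items needs no further change.

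The cost is SAP wording and one regression per outcome and time point, with no new visits, scans or samples. Against the uncontrolled TZ-arm paired test, the Day 1 detectable difference is 11% to 31% larger at correlations of 0.3 to 0.8, and somewhat more above that. Against the unadjusted t-test at weeks 6 and 12, the price is one degree of freedom and at most a 3% larger standard error at low correlation.

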We will randomize 20 PD patients to receive TZ or placebo. Ten of the participants will be randomized to receive TZ 5mg daily for 12 weeks and 10 participants will be randomized to receive a daily placebo for 12 weeks. This aim will generate data on safety and tolerability of TZ in a population of patients with PD. As an exploratory outcome, we aim to determine if treatment with TZ in patients with PD improves markers of energy metabolism. Furthermore, we will determine if cellular and cerebral ATP levels correlate with disease severity and progression. Participants will also participate in an assessment that will include, but is not limited to a motor exam, a neuropsychological assessment, and functional assessments. Clinical findings will be used to guide future clinical trials.

Interventions and Duration

Participants in this study will be randomized to receive either TZ 5 mg by mouth once daily or a matched placebo once daily. Once randomized, each participant will receive their assigned treatment for 12 weeks. Participants will be assessed via telephone for 3 weeks after their 2 week visit, then 6 weeks months after their baseline visit, then via telephone 9 weeks after their baseline visit, and their last visit will occur 12 weeks from their baseline visit. We anticipate that this study can be completed (study open to end of data analyses) within 9 months.

Sample Size and Population

This study will randomize 20 participants: 10 participants will be randomized to receive 5mg of TZ daily and 10 participants will be randomized to the placebo group. It is anticipated that no more than 35 participants will need to be screened to enroll these participants.

This study will include participants who are ≥ 40 years old who have a confirmed diagnosis of PD made by a neurologist and a Hoehn & Yahr score at baseline of < 4 . Participants will be excluded from this study if any of the following are true:

- Participants has orthostatic hypotension or a sitting blood pressure of $\leq 90/60$
- Participant is pregnant
- Participant has a deep brain stimulation device implanted
- Participant has a known allergy or sensitivity to terazosin
- Participant is concomitantly taking doxazosin, alfuzosin, prazosin, urapadil, or tamsulosin
- Participant has active drug or alcohol use or dependence that, in the opinion of the site investigator, would interfere with adherence to study requirements
- Participant is unable or unwilling to give written informed consent

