4.5.4 Randomization/Treatment Assignment

Participants will be randomized in a 1:1 fashion to TZ 5mg daily and placebo. Randomization will be performed by NuCara Pharmacy in Coralville, Iowa. Randomization codes will be made available only to the dispensing pharmacist. The randomization code will not be made available to the investigators, study centers, study subjects, or other representatives. Only after the study is complete, will randomization codes be made available to the investigators.

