6 CLINICAL AND LABORATORY EVALUATIONS/STUDY PROCEDURES

6.1 Schedule of Activities

Evaluation	Screening (-90 days)	Day 1	2 wks	3 wks	4 wks	5 wks	6 wks	9 wks	12 wks
Written Informed Consent	X								
Inclusion/Exclusion Review	X	X							
Documentation of Disease/Disorder	X	X							
Hoehn & Yahr	X	X	X				X		X
Medical History • Overall Medical History • Medical History of PD	X	X					X		X
Concomitant medication review	X	X	X				X		X
Orthostatics^a	X	X	X				X		X
MDS-UPDRS Motor assessment^b	X	X	X				X		X
Physical examination	X	X					X		X
Randomization^c		X							
Dispense Study Drug^d		X							
Blood Draw		X ^c					X		X
MRI		X ^c							X
Neurological examination	X	X					X		X
Body weight and height	X	X	X				X		X
Vital signs	X	X	X				X		X

Finger Tapping Assessments		X	X				X		X
Behavioral Assessments									

 Columbia Suicide Severity Rating Scale Questionnaire for Compulsive Disorders (C-SSRS) Beck Anxiety Inventory Beck Depression Inventory Parkinson's Disease Questionnaire (PDQ-39) 	X ^e	X	X ^f				X		X
Sleep assessment		X					X		X

 Pittsburgh Sleep Quality Index 									
Recent Falls			X	X	X	X	X	X	X
Cognitive Assessments		X					X		X

 Hopkins Verbal Learning Test (HVLT) Symbol Digit Modalities Test (SDMT) MoCa 									
Auditory/Speech Assessment		X	X				X		X
Pregnancy Test for Women of Child-Bearing potential	X	X	X				X		
Timed Up and Go Assessment		X	X				X		X
Drug Accountability/ Compliance			X	X	X	X	X	X	X
Adverse Event Review			X	X	X	X	X	X	X

a) Participants will lie in the supine position for 5 minutes and have their blood pressure checked. The patient will then sit up for 1 minute and have their blood pressure re-checked. The patient will then stand for 3 minutes and have their blood pressure checked. If the participant has a decrease in the systolic blood pressure by 20 or more mmHg after standing for 3 minutes, or a decline of 10 or more mmHg in the diastolic blood pressure, they will be considered to have orthostatic hypotension.

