9.1.3 Exploratory Outcome(s)

- Difference in ATP levels in red blood cells and brain within subjects before and after taking study drug on day 1
- Difference in ATP levels in red blood cells and brain within subjects at 6 and 12 weeks compared to baseline reading
- Difference in ATP levels in red blood cells and brain between groups at 6 weeks and 12 weeks
- Slope of change over 12 weeks of the MDS-UPDRS Part 1
- Slope of change over 12 weeks of the MDS-UPDRS Part 2
- Slope of change over 12 weeks of the MDS-UPDRS Part 3 (OFF)
- Slope of change over 12 weeks of the MDS-UPDRS Part 4 (OFF)
- Absolute change over 12 weeks of the MDS-UPDRS Parts 1, 2, 3, 4, and TMS (OFF)

FAST TZ-PD

Version 2.0

Version date: 11/12/2019

- Slope of change over 12 weeks of MDS-UPDRS TMS (OFF) (direct comparison for efficacy)
- Slope of change over 12 weeks of the Hoehn & Yahr Score
- Slope of change over 12 weeks of all cognitive assessments between placebo and active group
- Slope of change over 12 weeks of sleep assessments between placebo and active group
- Slope of change over 12 weeks of behavioral assessments between placebo and active group

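### The 12-week MDS-UPDRS change is compared by t-tests that ignore the baseline score; a baseline-adjusted week-12 difference would usually be more precise, by an amount that depends on an unstated correlation

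*Combined protocol and SAP*

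**What the plan says.** Section 9.4 lists, among the exploratory outcomes, "Absolute change over 12 weeks of the MDS-UPDRS Parts 1, 2, 3, 4, and TMS", to be analysed by "Independent samples t-tests". It names no covariate and gives no rule for a missing week-12 score. Section 9.1.3 confirms the exploratory status.

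The same section plans mixed-model (LMER) slopes for each part and for TMS, an abbreviation the documents do not expand. One slope is marked as the efficacy comparison: "Slope of change over 12 weeks of MDS-UPDRS TMS (direct comparison for efficacy"). The covariates, random effects and group-by-time term of these models are not given.

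On the analysis set, Section 9.4 states: "All randomized individuals will be included regardless of their final treatment status".

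The only MDS-UPDRS row in the Section 6.1 schedule is "MDS-UPDRS Motor assessment", at Screening (up to 90 days before Day 1), Day 1, and weeks 2, 6 and 12. The synopsis fixes the size: "10 participants will be randomized to receive 5mg of TZ daily and 10 participants will be randomized to the placebo group".

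**The concern.** A t-test on change subtracts the whole baseline score, whatever the correlation between baseline and week 12. When that correlation is well below 1, the subtraction adds noise that regression on baseline would avoid. The baseline motor score is already scheduled, so the adjustment needs no new visit.

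A t-test on 12-week change also has no value to use for someone without a week-12 score, and the plan does not say what happens then. Sections 6.2.3 and 6.2.4 disagree on whether those who stop study drug are followed to the end, and Section 4.4 does not replace withdrawals, so such gaps are foreseeable.

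The synopsis says the clinical findings will inform later trials. With no power calculation behind the sample size, the estimates and their intervals are what this outcome can contribute.

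**Working it through.** **Inputs.** n = 10 per arm, N = 20 (synopsis; 1:1 allocation in Section 4.5.4). Section 9.2 bases the size on funding and resources and gives no SD, effect, alpha or power, so there is no planned figure to reproduce. Assumed: equal SD at both visits (set to 1); r from 0.5 to 0.9; two-sided 5% level.

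**Formulas for the variance of the between-arm difference.**
- Change score: 2(1 − r) × 2/n.
- ANCOVA on one baseline: (1 − r²) × 2/n × (N − 3)/(N − 4). The last factor, 17/16 = 1.0625, is the small-sample cost of the covariate.
- Ratio, ANCOVA to change score: (1 + r)/2 × 17/16.

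| r | Change score | ANCOVA | Ratio | Power for a 1 SD effect | Detectable difference at 80% power (SD) |
|---|---|---|---|---|---|
| 0.5 | 0.200 | 0.159 | 0.80 | 56% → 66% | 1.33 → 1.19 |
| 0.7 | 0.120 | 0.108 | 0.90 | 78% → 82% | 1.03 → 0.98 |
| 0.8 | 0.080 | 0.077 | 0.96 | 92% → 93% | 0.84 → 0.82 |
| 0.9 | 0.040 | 0.040 | 1.01 | no gain | 0.593 → 0.597 |

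Power uses the noncentral t with 18 and 17 degrees of freedom. A simulation of 20,000 trials per r gave ratios of 0.79, 0.90, 0.95 and 1.01. Break-even is where (1 + r)/2 × 17/16 = 1, that is r = 32/17 − 1 = 0.88.

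**Using both motor exams.** If Screening, Day 1 and week 12 are all equally correlated, ANCOVA on the mean of the two pre-dose exams has ratio (1 + 2r)/(2(1 + r)) × 17/16 = 0.71, 0.75 and 0.78 at r = 0.5, 0.7 and 0.9. An unadjusted change from that mean has variance 1.5(1 − r) × 2/n, already 0.75 of the planned comparison, so almost all of this gain comes from averaging.

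Now let correlation decay with time, as r^(days/84), with Screening 90 days before Day 1 and so 174 days before week 12. With a = r^(90/84) and b = r^(174/84), the ratio is [1 − (r + b)²/(2(1 + a))] × 17/16 ÷ [2(1 − r)]. At r = 0.7, a = 0.682 and b = 0.478, giving 0.588 × 1.0625 ÷ 0.6 = 1.04. At r = 0.5 and 0.9 it is 0.87 and 1.24. All three are worse than Day 1 alone (0.80, 0.90, 1.01).

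**Missing week 12.** If one or two per arm have no usable value, the t-test's power for a 1 SD effect at r = 0.5 falls from 56% to 51% or 46%. An ANCOVA restricted to week-12 completers loses the same people; a mixed model does not.

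**Which baselines exist.** The motor exam has its own schedule row. Parts 1 and 2 (Section 6.3.12) and Part 4 (Section 6.3.8) are described but have no row. A schedule footnote places Day 1 baseline assessments before randomization, whereas Section 6.2.1 allows other assessments in the three hours after the first dose.

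**The case against.** The strongest reply is that the plan already contains a better analysis. The LMER slopes can use intermediate visits and people without week 12, and the TMS slope is the one marked for efficacy. The t-tests are a companion exploratory analysis in a safety and feasibility pilot, and they are unbiased under randomization. This stands and limits the point. It does not remove it, because the t-tests remain a separate listed result and the LMER specification is left open.

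Four stronger readings are tempting, and the documents do not support them.
- *The trial wastes precision on its efficacy comparison.* The LMER slopes contradict this.
- *Anyone without a week-12 score is excluded, in breach of intention to treat.* The inclusion sentence concerns treatment status. Sections 4.4, 6.2.3 and 6.2.4 all seek a final evaluation, and that value might be used. What is missing is a rule.
- *Averaging the two motor exams is worth 28 to 41% more patients for nothing* (1/0.78 to 1/0.71). This needs equal correlation across a gap of up to 90 days. Section 4.1 requires a stable dopaminergic regimen only for the 4 weeks before baseline, so the Screening exam may reflect a different one.
- *Chance imbalance spoils the t-test.* The arms do differ at baseline by more than 0.5 SD with probability 2(1 − Φ(0.5/√0.2)) = 26%. But a change score already subtracts baseline, and the residual is (1 − r) × 0.5 SD: 0.15 SD at r = 0.7 and 0.05 SD at r = 0.9.

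**Conclusion.** The point holds with limited reach. One exploratory analysis uses a comparison that is less precise than a baseline-adjusted one unless r exceeds about 0.88. The saving is about 20% of variance at r = 0.5, 10% at 0.7 and 4% at 0.8, with a loss of about 1% at 0.9. These figures assume equal SDs and an r that the documents do not give.

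Any further gain from the Screening motor exam is conditional: a ratio of 0.71 to 0.78 under equal correlation, and no gain or a loss from an equal-weight mean under serial decay. The claim is secure for the motor part only, and for TMS only if it needs no other part.

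**What to change.** In Section 9.4, replace the t-tests by the week-12 between-arm difference with a 95% CI, adjusted for the pre-dose Day 1 score. Use ANCOVA or, to keep participants with partial follow-up in line with the stated analysis set, a mixed model over visits with a common pre-dose mean in both arms. Fit the mixed model by REML with Kenward-Roger or Satterthwaite degrees of freedom.

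For the motor part, the Screening OFF exam may enter that model as a second pre-dose measurement with its correlation estimated. Do not force an equal-weight mean. An unstructured covariance has 10 parameters for four visits (4 × 5/2) and 15 for five (5 × 6/2), so name a simpler fallback for N = 20.

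Also:
- state how a missing week-12 score and an early final-visit score are handled;
- reconcile Sections 6.2.3 and 6.2.4 on follow-up after stopping drug;
- reconcile the Section 6.1 footnote with Section 6.2.1 on whether Day 1 assessments precede the first dose;
- show in the schedule when Parts 1, 2 and 4 are collected, and define TMS.

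Section 9.4 names no analysis for blood pressure change, although Section 9.1.2 lists it as a secondary outcome. The same baseline-adjusted model could be specified there; it would replace no stated test.

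The cost is wording, one degree of freedom for ANCOVA, and about 1% of variance if r is near 0.9. The motor part needs no new visit.
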